# **LIST OF ABBREVATIONS**

AE Adverse Event

AEV Electro-Acupuncture according to Voll

BMI Body Mass Index

CRF Case Report Form

CRO Clinical Research Organisation

EC Ethical Committee

ICF Informed Consent Form

GCP Good Clinical Practice

SAE Serious Adverse Event

TMF Trial Master File

#### **PROTOCOL SUMMARY**

**Title:** Clinical evaluation of the accuracy of Vitastiq device for tracking vitamin

and mineral trend in human body

Study acronym: VITASTIQ

Protocol No.: VITA-01

Protocol version: 1.0

**Study design:** The single site evaluation study will include 45 subjects who will test

Vitastiq device for 57 days. On day 1, 29 and 57, participants' blood sampling will be collected and analysed, and measurements using Vitastiq device will be performed. Data will be analysed retrospectively to evaluate Vitastiq performance compared to blood test results.

to evaluate vitastiq performance compared to blood test results.

**Study population:** Healthy women and men in ratio 1:1 (approximately), aged between 18

and 64 years will be included in the study.

Number of participants: 45

**Study coordinator:** Vizera d.o.o., Slovenia

**Study Sponsor:** Vitastiq d.o.o., Croatia

**Study center:** Adria lab d.o.o., Ljubljana

**Study period:** First patient in to last patient out (months): 6

Duration of the study (months): 2 Recruitment period (months): 4

FPFV: May 2017

LPLV: November 2017

Inclusion criteria:

• Informed consent form (ICF) is signed by a volunteer

Age between 18 and 64 years at the time of the signature of ICF

A body mass index (BMI) between 18 and 28 kg/m^2

Healthy, meaning absence of any chronic or acute medical therapy

for a month prior to the inclusion to the study

Willing to follow all study procedures, including attending all site visits,

and keeping a food diary and diary of activities on a weekly basis

**Exclusion criteria:** • Intake of any drugs to treat chronic disease within 1 month before

the beginning and during the study

 Intake of any drugs to treat serious acute disease within 1 month before the beginning of the study and within 5 days of each visit

- Any clinically significant medical history of serious digestive tract, liver, kidney, skin or haematological disease or hormone imbalance
- Pregnant and breastfeeding women
- Women who planning pregnancy during the study
- Inadequate veins (in the opinion of the investigator)
- Known drug or alcohol abuse
- Using any form of nicotine or tobacco
- Mental incapacity that precludes adequate understanding or cooperation
- Participation in another investigational study or blood donation within 3 months prior to or during this study

Study objectives:

The main objective is to define the accuracy of Vitastiq device readings.

**Study endpoints** 

The **primary endpoint** of the study is to determine the Vitastiq device accuracy and performance. The goal is to achieve at least 70% Vitastiq accuracy performance meaning that at least 70% of Vitastiq readings for each mineral and vitamin fall within the range of matching blood test results.

The **secondary endpoint** of the study is to define repeatability of Vitastiq readings method. The goal is to achieve at least 80% Vitastiq readings method repeatability meaning that at least 80% of Vitastiq readings for each mineral and vitamin performed by less experienced investigator and participant fall within the range of matching Vitastiq readings performed by the most experienced investigator.

Statistical analysis

Statistical analysis of primary study outcome will be based on calculation of 95% confidence interval (CI) of the estimated accuracy of Vitastiq readings for each mineral or vitamin. The expected accuracy level is 70%, therefore by using 135 readings the radius of 95% confidence interval would be estimated with 10% relative margin of error. The point estimate of the accuracy value together with 95% CI will be presented for each mineral or vitamin

Statistical analysis of secondary outcomes will include Kappa statistic for interrater reliability on Vitastiq readings or Friedman ANOVA for testing the possible change of each mineral/vitamin blood level during the study period. Kappa statistic for interrater reliability will be calculated separately for each analyte and for all 135 readings. Additionally, the results of the second and the third rater (second investigator and participant) will be separately compared to the results of the first rater (first investigator). In Friedman ANOVA test 3 consecutive blood test results, that is on day 1, 29, and 57, will be compared.

## 1. INTRODUCTION

Poor dietary choices not only manifest in obesity, which is currently the main public health focus in the world, but can also lead to inadequate micronutrient intakes, with implications for health. Recent dietary survey data and measurements of status biomarkers have highlighted folate, vitamin D, calcium, iron and iodine to be amongst the micronutrients of most concern [1]. in order to anticipate and prevent the health consequences of micronutrient deficiencies, an easy and cost effective way of determining and tracking vitamin and mineral status is of particular importance.

Vitamin and mineral status in our body can be obtained in several ways. The most common and well acceptable way is to assess vitamin and mineral concentration from blood serum or plasma. Results obtained by these well-established analytical methods require professional explanation. An alternative to blood testing is Electro-Acupuncture method according to Voll (EAV). EAV has been used for decades in pharmacies and specialist offices. It is based on the acupuncture energy meridians theory and Reinhold Voll's electro-acupuncture research.

#### 1.1 BACKGROUND AND SCIENTIFIC BASIS FOR THE STUDY

In 1950's, a German medical doctor, Internal Medicine specialist, and engineer, [name], began researching and proving the diagnostic and therapeutic benefits of an innovative testing method now known as EAV (Electro-Acupuncture according to Voll). The EAV method [2] is used to assess the individual's energy with a painless and non-invasive procedure. These are acupoints and a system of meridians, a network of energy channels connected among each other and to parts of the body or organs. Electro-Acupuncture according to Voll is a big part of the Meridian Stress Assessment (MSA) which focuses on measuring organs in the body. They are either balanced, weakened or stressed.

EAV measurement device consists of the patient holding a negative electrode on his or her hand and the practitioner touching the body with a stylus. The EAV device generates a safe electric current. [name] saw that testing electrical conductance at specific acupoints had a higher electrical flow than other locations. [name] soon discovered that when an internal organ's function or structure changes, the performance of the related meridian and acupuncture points also changed, and that this change could be measured using a device.

In modern devices used in this type of assessment the voll machine comes with specialized software. This can lead to a support protocol for stressed or weakened organs along with reports about the final results.

This method was documented and tested in over a decade of hospital studies in Germany [3-5]. EAV is part of alternative and holistic medicine techniques to help determine the body's health imbalances and it is widely used throughout Europe and the world [6].

## 1.2 INVESTIGATIONAL DEVICE (ID)

An EAV device is a type of Electrical Conductivity Meter and is considered to be safe [7]. The newer generation devices have specialized software but, essentially, any EAV device is a Conductivity Meter.

In using an EAV device, each Meridian Point is tested with a Point Probe (a positive electrode [+]). Regardless of age, weight, sex or race of testing individuals, a reading of 50 with no change over time (no indicator drop) is an indication of an Energetically healthy or »Balanced« meridian. Readings at points that are significantly above 50 (65+) indicate »Irritation« of the Meridian. Readings above 75 exhibit »Inflammation« of the Meridian. When a reading is significantly lower than 50 (below40) then is believed that this meridian is displaying »low energy« properties.

One of EAV devices is Vitastiq device for personal use. It helps indicate the user's vitamin and mineral trend. The accompanying user-friendly Vitastiq app saves the history of previous readings to allow Vitastiq users to keep track of their progress.

Vitastiq is a single innovative hardware and software concept that provides a personalised way of measuring vitamins and minerals through a smartphone.

It measures the vitamin or mineral content in the skin at various acupuncture points that are outlined on the body and then displays the information on the smartphone screen as LOW, NORMAL or HIGH. Results are achieved by measuring the electrical status of the skin. The Vitastiq mobile app saves and evaluates the history of readings, which enables the user can keep track of the progress.

Today EAV is widely used throughout Europe by over 25,000 medical practitioners [8]. However, there is still a lack of reliable data obtained by clinical trials that would show the reliability and/or accuracy preferences of individual EAV device. It thus causes doubts and resistance to use EAV for personal or professional use. Therefore, we would like to define accuracy of Vitastiq device, a vitamin and mineral trend tracker.

#### 1.3 STUDY PURPOSE

The purpose of the study is to test the accuracy of Vitastiq device as a personal tracker of vitamins and minerals in human body and to obtain and analyse data to enhance the accuracy of new version of Vitastiq device.

The main objective is to define the accuracy of Vitastiq device. Data (readings) obtained by Vitastiq will be compared to blood test results obtained by commonly used analytical methods. Both, Vitastiq readings and blood sampling will be taken at the same time. Vitastiq accuracy performance for each mineral and vitamin reading is considered acceptable if at least 70% of Vitastiq readings fall within the range of matching blood test results.

The study should provide answers to two main questions:

- a) Do 70% of Vitastiq readings for each mineral and vitamin fall within the range of matching blood test results?
- b) Is Vitastiq reading method at least 80% repeatable where the readings performed by the most experienced investigator are compared to the readings performed by less experienced investigator and participant.

## 2. STUDY DESIGN

#### 2.1 DESCRIPTION OF THE STUDY DESIGN

This is a single site evaluation study of Vitastiq device accuracy in healthy men and women over the age 18. A total of 45 Vitastiq personal devices will be used by volunteers for two months. The Vitastiq device will be evaluated during three site visits: on day 1,  $29 \pm 4$  days and  $57 \pm 4$  days and  $54 \pm 4$  home use days (every day between first and last day of the study except on visit days). During site visit days, blood sampling will be collected and analysed and readings using Vitastiq device will be performed. Data will be analysed retrospectively to evaluate Vitastiq performance compared to blood tests results.

Participant will complete a home diary which will include all readings for selected minerals and vitamins once per day – in the mornings, after waking up. Subject's will report about physical activities, and food intake during every week.

Some participants may not complete a full 57-day (± 4 days) study period for various reasons, such as the device failure. All device failures or problems will be documented.

#### 2.2 STUDY ENDPOINTS

## 2.2.1 Primary endpoint

The primary endpoint of the study is to determine the Vitastiq device accuracy and performance. The goal is to achieve at least 70% Vitastiq accuracy performance meaning that at least 70% of Vitastiq readings for each mineral and vitamin fall within the range of matching blood test results. Vitastiq readings will be presented as low, normal and high, where:

- low means below the agreed normal level for selected mineral or vitamin determined by biochemical blood analyses tests (see Table 1)
- normal means within the range of agreed normal level and
- high means above the agreed normal level.

Data will be collected from Vitastiq device utilizing 45 volunteers. Volunteers will visit the site three times (day 1,  $29 \pm 4$  days and  $57 \pm 4$  days). Three complete Vitastiq readings by two investigators (who differs in years of experiences in performing EAV by Vitastiq device) and by the participant in the study will be performed at each visit (altogether, 405 Vitastiq readings will be collected on visit days (day 1,  $29 \pm 4$  days and  $57 \pm 4$  days) for 45 volunteers). To confirm the primary endpoint only Vitastiq readings performed by the most experienced investigator in acupuncture will be taken to evaluate the accuracy. Therefore, 135 Vitastiq readings taken on visit days (day 1,  $29 \pm 4$  days and  $57 \pm 4$  days) will be compared to blood test results. Analyses of Vitastiq data generated by matching minerals and vitamins levels to venous blood minerals and vitamins concentration by well-established analytical methods on day 1,  $29 \pm 4$  days and  $57 \pm 4$  days will determine Vitastiq device accuracy and performance.

Table 1: Agreed normal levels of vitamins and minerals in blood serum (fasting).

Mineral/Vitamin	Low	Normal	High	
Sodium	< 135 mmol/L	135 – 145 mmol/L	> 147 mmol/L	
Potassium	< 3.8 mmol/L	3.8 – 5.5 mmol/L	> 5.5 mmol/L	
Calcium	< 2.15 mmol/L	2.15 – 2.55 mmol/L	> 2,55 mmol/L	
Magnesium	0,66 mmol/L	0,66 – 1,07 mmol/L	> 1,07 mmol/L	
	Men: < 10,6 μmol/L	Men: 10,6 – 28,3 μmol/L	Men: > 28,3 μmol/L	
Iron	Women: < 6,6 μmol/L	Women: 6,6 – 26,0 μmol/L	Women: > 26,0 μmol/L	
Zink	< 70 μg/dL	70 – 150 μg/dL	> 150 μg/dL	
Selenium	< 50 μg/L	50 – 120 μg/L	> 120 μg/L	
Folic acid	< 7,0 nmol/L	7,0 – 46,4 nmol/L	> 46,4 nmol/L	
Vitamin A	< 250 μg/L	250 – 1100 μg/L	> 1100 μg/L	
Vitamin B12	< 138 pmol/L	138 – 652 pmol/L	> 652 pmol/L	
Vitamin D	< 30 μg/L	>30 µg/L	/	
Vitaria E	Men: < 8,9 mg/L	Men: 8,9 – 18,3 mg/L	Men: > 18,3 mg/L	
Vitamin E	Women: < 9,4 mg/L	Women: 9,4 – 15,0 mg/L	Women: > 15,0 mg/L	

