# 8. STATISTICAL DESIGN AND METHODS

Statistical analysis of primary study outcome will be based on calculation of 95% confidence interval (CI) of the estimated accuracy of Vitastiq readings for each mineral or vitamin. The expected accuracy level is 70%, therefore by using 135 readings the radius of 95% confidence interval would be estimated with 10% relative margin of error. The point estimate of the accuracy value together with 95% CI will be presented for each mineral or vitamin.

Statistical analysis of secondary outcomes will include Kappa statistic for interrater reliability on Vitastiq readings or Friedman ANOVA for testing the possible change of each mineral/vitamin blood level during the study period. Kappa statistic for interrater reliability will be calculated separately for each analyte (vitamin and mineral) and for all 135 readings. Additionally, the results of the second and the third rater (second investigator and participant) will be separately compared to the results of the first rater (first investigator). In Friedman ANOVA test 3 consecutive blood test results, that is on day  $1, 29 \pm 4$  days and  $57 \pm 4$  days, will be compared.

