## 9. DATA ANALYSIS AND REPORTING

#### 9.1 STATISTICAL DATA ANALYSIS

The detailed statistical analysis will be outlined in a separate statistical analysis plan and executed by the statistician.

Participant demographics and baseline characteristics will be presented using appropriate summary statistics (mean, standard deviation, median, minimum and maximum for continuous variables; frequency counts and percentages for categorical variables). Number of enrolled volunteers and number of completed visits will be reported. An overview of study discontinuations will be provided.

No interim analysis will be performed in this study.

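### Table 1 ends sodium NORMAL at 145 mmol/L but starts HIGH above 147 mmol/L, which conflicts with the text's definition of high and leaves part of the primary endpoint's scoring key unsettled

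*Combined protocol and SAP*

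**What the plan says.** Section 2.2.1 (Primary endpoint) sorts results into three categories relative to an agreed normal level, and its definition of low points to Table 1 for that level. The other two definitions are "normal means within the range of agreed normal level" and "high means above the agreed normal level". Read alone, this is a complete rule: every value is below, within or above the normal level.

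The sodium row of Table 1 in the same section reads: low, below 135 mmol/L; normal, 135 to 145 mmol/L; high, above 147 mmol/L.

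The goal applies analyte by analyte: "at least 70% of Vitastiq readings for each mineral and vitamin fall within the range of matching blood test results". Only the most experienced investigator's readings count, which gives 135 per analyte. Section 8 adds that "The point estimate of the accuracy value together with 95% CI will be presented for each mineral or vitamin". Section 9.1 states that "The detailed statistical analysis will be outlined in a separate statistical analysis plan"; that plan was not among the documents supplied.

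**The concern.** Table 1 is the key by which a device reading is called a match or a mismatch. For sodium, the text and the table disagree about results above 145 and up to 147 mmol/L, and nothing else in the protocol says how to score them.

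Sodium has its own 70% goal and its own confidence interval, so the choice of limit enters one of the primary results directly. Section 2.1 says the data will be analysed retrospectively. If the limit is still open when device and blood results are put side by side, it could be chosen with the results in view.

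**Working it through.** **1. Is sodium the only row with a gap?** For each row of Table 1, subtract the upper end of normal from the start of high.

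| Row | Normal ends | High starts above | Gap |
|---|---|---|---|
| Sodium | 145 | 147 | 2 |
| Potassium | 5.5 | 5.5 | 0 |
| Calcium | 2.55 | 2.55 | 0 |
| Magnesium | 1.07 | 1.07 | 0 |
| Iron, men | 28.3 | 28.3 | 0 |
| Iron, women | 26.0 | 26.0 | 0 |
| Zinc | 150 | 150 | 0 |
| Selenium | 120 | 120 | 0 |
| Folic acid | 46.4 | 46.4 | 0 |
| Vitamin A | 1100 | 1100 | 0 |
| Vitamin B12 | 652 | 652 | 0 |
| Vitamin E, men | 18.3 | 18.3 | 0 |
| Vitamin E, women | 15.0 | 15.0 | 0 |

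Vitamin D has no high limit and is not counted. The 12 pairs other than sodium (10 analytes, two of them with separate limits by sex) all meet exactly. No sentence describes a borderline band for sodium.

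**2. How is a gap result scored?** Take a blood sodium above 145 and up to 147 mmol/L.

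| Device reading | Limit 145 (blood is high) | Limit 147 (blood is normal) |
|---|---|---|
| LOW | mismatch | mismatch |
| NORMAL | mismatch | match |
| HIGH | match | mismatch |

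If *a* gap results are read NORMAL and *b* are read HIGH, the count of matches under 147 minus the count under 145 is *a* − *b*. The difference is largest when all gap results get the same one of these two readings.

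**3. What is each result worth?** The plan's count is reproduced: 45 volunteers × 3 visits = 135 readings. One reading is 1/135 = 0.74 percentage points. Since 94/135 = 69.6% and 95/135 = 70.4%, the goal needs 95 matches. The choice of limit changes whether the goal is met only if one count is 95 or more and the other is 94 or fewer.

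**4. How many results might fall in the gap?** The documents do not say, so this step rests on assumptions: sodium normally distributed with mean 140 mmol/L (the midpoint of 135 to 145) and SD from 2 to 2.55 mmol/L. The upper SD is the value that makes 135 to 145 a central 95% range: 5/1.96 = 2.55.

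Expected count = 135 × P(145 < x ≤ 147) for continuous results, or 135 × P(145.5 < x ≤ 147.5) if results are reported as whole numbers.

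| SD (mmol/L) | Continuous | Whole numbers |
|---|---|---|
| 2 | 0.81 | 0.39 |
| 2.25 | 1.65 | 0.92 |
| 2.5 | 2.73 | 1.69 |
| 2.55 | 2.96 | 1.87 |

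These are means, not limits. By a Poisson approximation, more than 3 gap results would occur with probability about 34% at a mean of 2.96 and about 12% at a mean of 1.87. Each volunteer gives three samples, and clustering within person could widen the spread.

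**5. Illustration.** Suppose 3 results fall in the gap, the device reads all of them NORMAL, and the count under 147 is 95. Then, with Wilson 95% intervals:

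- limit 147: 95/135 = 70.4% (62.2% to 77.4%)
- limit 145: 92/135 = 68.1% (59.9% to 75.4%)

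The point estimate crosses 70%, but the two intervals overlap almost entirely.

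**The case against.** The strongest reply is that the text already settles the matter. It gives a complete rule, Table 1 is titled as a list of agreed normal levels, and the sodium normal cell ends at 145, so a result of 146 is high and nothing is left without a category. This has force, but it holds only if the normal cell is the correct one. The documents do not show which cell is wrong, and an analyst coding directly from the table would find no category for the gap.

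A second reply is that the conflict rests on one digit in a table read by a program, and the table shows other damage, such as a garbled vitamin E label. A misread digit cannot be fully excluded. The sodium row is otherwise intact, and a look at the source would settle it.

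A third reply is that the consequence is slight: one of 12 analytes is affected, Section 8 plans estimation with an interval rather than a formal test, and the separate analysis plan may already fix the limit. All of this stands, and it is why the point is minor.

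A reader might go further than the documents allow in two ways. One is to infer that gap results would be left uncategorised and dropped from the denominator; no section provides for excluding such readings. The other is to treat about 3 gap results, or about 2 percentage points, as the most that could be at stake; those figures are expectations under an assumed distribution, not a ceiling.

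**Conclusion.** The contradiction is real on the text supplied: the definition of high and the two sodium cells cannot all be right. One of the two cells is probably a slip, but the documents do not say whether it is 145 or 147. Severity is minor.

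The firm part of the size is 0.74 percentage points per re-scored result against a pass mark of 95 of 135. The number of results in the gap is unknown; the rough expectation of 0.4 to 3 depends wholly on the assumed mean and SD. The effect is probably small, and it can alter whether the goal is met only when sodium accuracy lies close to 70%. That is also the accuracy Section 8 expects, so such a result is not far-fetched. The documents do not support a wider inference that the primary endpoint as a whole is compromised, since the results for the other analytes do not depend on this row.

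**What to change.** Before device and blood results are compared, check the sodium row against its source and reconcile the 145 and 147 limits with each other and with the definitions in Section 2.2.1, so that every sodium result has exactly one category. Carry the same limit into the separate analysis plan, or confirm that the plan already states it.

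If the comparison has already been made, report sodium accuracy and its 95% confidence interval under both limits and state how many results fell in the gap.

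The cost is a correction to one table cell. No new data are needed, because Section 2.2.2 shows that blood results are obtained as numbers. The only downside is that the sodium result may shift slightly from what one of the two limits would have given.
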